The PARTNER (I) trial was the first of its kind to randomize patients to THV versus the current standard of care, and has produced the most conclusive evidence of the safety and effectiveness of the Edwards SAPIEN THV in both high risk surgical (Cohort A) and inoperable patients with symptomatic aortic stenosis (Cohort B). Cohort B randomized patients between medical therapy and transfemoral (TF) TAVI. The one-year results for survival and functional improvements in both New York Heart Association (NYHA) class and Quality of Life indices indicated that TAVI should be the new standard of treatment for patients with severe AS considered to be at too high a risk to undergo surgical AVR [24, 35]. Recent results support the sustained benefit up to five years post TAVI [19, 21, 36].

The Cohort A randomized TAVI to AVR in patients who were considered at high operative risk for surgery based on the STS score [37]. While peri-procedural stroke rates were higher in the TAVI arm (3.8% vs. 2.1% [p=0.20]), the overall composite endpoint of all-cause mortality or stroke at 1 year was not different between the two arms (24.2% for TAVI vs. 26.8% for AVR (difference -2.6%, 95% upper confidence limit 3.0%, pre-defined margin 7.5%; p = 0.001 for non-inferiority). Moreover, despite the initial higher 30-day stroke rate in the TAVI arm, the mortality at 30 days was numerically lower in the TAVI arm (3.4% vs. 6.5% for TAVI and AVR, respectively). This difference did not reach statistical significance, however (p=0.07). Major vascular complications were more frequent after TAVI (11.0% vs. 3.2%, P<0.001), whereas major bleeding (9.3% vs. 19.5%, P<0.001) and new-onset atrial fibrillation (8.6% vs. 16.0%, P<0.001) were more frequent after AVR. Both NYHA Class and Quality of Life index improvements favoured TAVI at 30 days, but were similar after 1 year. Paravalvular aortic regurgitation (PAR) was more frequent after TAVI than AVR (P<0.001), and a late association between residual PAR and mortality has been subsequently revealed [21].

Three year data demonstrate sustained benefits for aortic valve replacement in both the TAVI and AVR arms with the SAPIEN valve demonstrating a sustained durability similar to surgical bioprostheses with no differences in long term mortality (44.2 vs. 44.8%, for TAVI vs. AVR, respectively)[38].

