Conclusions from the first randomized Edwards SAPIEN THV studies indicate that balloon expandable TAVI should be recognized as the standard of care for inoperable patients and is an

acceptable alternative to AVR in high risk patients. Also reported were significant outcomes related to the study device versus standard therapy control, such as stroke, major vascular complications and major bleeding events which had significant impact on overall mortality. These findings were consistent with earlier published reports. Despite the high-risk nature of the population studied, it is a widely held belief that design improvements in the profile and ease of use of the delivery system may reduce procedure-related adverse events and thus support expansion of the study population to include patients previously excluded due to anatomical limitations. Two year data from the SOURCE XT post-approval study of the SAPIEN XT demonstrate similar long-term performance to the SAPIEN valve [39], with more favourable long-term survival for patients presenting with few comorbidities at baseline. The SAPIEN 3 is the most recent SAPIEN THV to obtain the CE Mark (January 2014). The SAPIEN 3 has been designed to be placed via a fully percutaneous TF approach using the Edwards Expandable Sheath ("eSheath"), and its TF delivery has demonstrated the lowest rates of death, stroke, and major vascular complications (2.1, 1.0 and 4.2%, respectively) for any SAPIEN THV [40]. The robust body of consistently improving clinical evidence presented by Edwards SAPIEN transcatheter valve platforms attests to the Edwards history of leadership in heart valve bioprosthesis technology.

3. Study Device

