4.1 Primary Endpoint

The primary endpoint is all-cause mortality at 30 days post-index procedure.

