4.2 Secondary Endpoints

Safety

- Cardiovascular mortality at 30 days
- Stroke at 30 days
- TIA at 30 days
- All-cause mortality & stroke at 30 days
- Vascular complications (major) at 30 days
- Bleeding complications (life threatening or disabling, and major) at 30 days
- Myocardial infarction at 30 days
- Acute kidney injury at 30 days (stages II and III)
- Coronary obstruction requiring intervention at 30 days
- Permanent pacemaker implantation at 30 days

Device Success

- Absence of procedural mortality AND
- Correct positioning of a single prosthetic heart valve into the proper anatomic location AND
- Intended performance of the prosthetic heart valve (no prosthesis-patient mismatch and mean aortic valve gradient <20mmHg or peak velocity <3m/s, AND no moderate or severe prosthetic valve regurgitation) at 30 Days

Efficacy

- New York Heart Association (NYHA) Classification at 30 days
- Hemodynamic valve performance evaluation by echocardiography for aortic valve stenosis and aortic valve regurgitation (paravalvular & central) at 30 Days as determined by Echo core lab

5. Patient Population

To ensure that a minimum of 50 patients are implanted with the SAPIEN XT THV and complete the 30 Day follow-up for Primary Endpoint, up to 60 patients will be enrolled and implanted with SAPIEN XT THV. Each site may not contribute more than 30 implanted patients to the study population. All patients will be followed for 5 years.

Enrolment will be closely monitored to ensure not more than 60 patients are implanted with SAPIEN XT THV.

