6.3.3.6 Follow-Up Visits

The determination of the study endpoints will require rigorous clinical follow-up and quality data collection. The Investigator or delegated study personnel will ensure the patient is scheduled for follow-up visits according to Table 6.

Table 5Follow-up Visit Windows.

| Follow-Up Visit | Visit Window (days following Procedure) |
|-----------------|---|
| 30 Day | 30 days, +14 days |
| 6 Month | 180 days +/-30 days |

| 1 Year | 365 days +/-60 days |
|--------|----------------------|
| 2 Year | 730 days +/-60 days |
| 3 Year | 1095 days +/-60 days |
| 4 Year | 1460 days +/-60 days |
| 5 Year | 1825 days +/-60 days |

The importance of attending the 30 Day follow-up visit should be discussed with the patient. Planned absences should be recorded to facilitate continued ability to contact a study patient during the course of the study. If a patient cannot be reached for a follow-up visit, the investigator will document on the follow-up data form, the efforts undertaken to contact the patient, referring physicians, including internists as well as cardiologists, family members, or other alternate contacts noted in the study patient's records. These efforts should include 3 attempts of telephone contacts at separate dates and times, and a registered letter. If a patient can no longer be located, the investigator must contact an intermediary (e.g. patient's private physician) without delay.

Patients for whom the study procedure was begun but do not receive and retain the study valve will be followed up until the 30-day assessment or resolution of any AE for safety purposes. Patients with an ongoing AE at the 30 Day visit should have AEs reassessed at 30 day window closure (day 44). These patients should then be exited from the study. In the event that the patient's implanted valve is explanted, the patient needs to be followed up until resolution of any AE for safety purposes. These patients should then be exited from the study.

6.3.3.6.1 30-Day Visit

All patients will undergo the following assessments within the 30-Day follow-up period +14 days):

- Pertinent physical examination [include blood pressure, weight and all major systems findings]
- Adverse events
- Current cardiac medications and all medications given for cardiovascular effect
- NYHA functional classification
- CSS Angina Classification
- Neurological assessments
 - o NIHSS
 - o MRS
- 6 Minute Walk Test (6MWT)
- Clinical Laboratory Test

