11.3 Analysis Sets

- As Treated (AT) Population: all patients that were enrolled in the trial for whom the SAPIEN XT valve implant procedure was begun, defined as the time in which the first Edwards' investigational device is inserted into the patient.
- *Valve Implant (VI) Population:* all AT patient who received and retained the SAPIEN XT valve upon leaving the procedure room

All patients documented as part of the roll-in patient strategy will not be included in analysis population and evaluated separately.

The primary and secondary endpoints will be reported based on the AT Population. AT patients that did not receive the SAPIEN XT valve will be censored at 30 days or at resolution of any AE.

Descriptive and summary statistical analysis will be performed on all endpoints. Patient listings for adverse events, deaths, and reinterventions will include all enrolled patients.

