11.5 Endpoint Analysis

Patient data listings and tabular and graphical presentations of results will be provided. All clinically relevant baseline and follow-up variables will be tabulated. Descriptive statistics will be used for continuous variables (e.g., mean, standard deviation, sample size, minimum, and maximum) and frequency tables or proportions for discrete variables.

Kaplan Meier estimates will be performed at the pre-specified follow-up times to project the estimates for time-related safety endpoints. The Kaplan-Meier analysis will be used to compute the 30-day mortality rate, the primary endpoint; the standard error and confidence limits will be computed using Greenwood's algorithm.

Echocardiographic data will be analyzed by an Echo core laboratory with respect to the degree of total aortic valve regurgitation (TVR) and paravalvular aortic valve regurgitation (PAR) according to the VARC-2 definitions [46].

These data and other categorical data (e.g., NYHA class) will also be presented as shift from baseline for each of the pre-specified follow-up periods.

More specific information regarding the statistical analysis will be presented in the Statistical Analysis Plan (SAP).

12. Study Administration

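### Greenwood confidence limits for 30-day mortality collapse to 0%-0% or are undefined if no patient dies, a realistic result with 50-60 patients

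*Combined protocol and SAP*

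**What the plan says.** Section 4.1 defines the endpoint: "The primary endpoint is all-cause mortality at 30 days post-index procedure". Section 11.5 computes the 30-day rate by Kaplan-Meier and adds that "the standard error and confidence limits will be computed using Greenwood's algorithm". It names no confidence level, no transformation and no alternative for zero or few deaths. Section 11.4 (Missing Data) adds nothing on this, and Section 11.5 leaves further detail to a SAP whose text is not in the combined document.

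Section 11.1 sets the sample size at 50-60 by regulatory agreement, without a calculation. Section 5 gives the purpose of the range: "To ensure that a minimum of 50 patients are implanted with the SAPIEN XT THV and complete the 30 Day follow-up for Primary Endpoint". The ceiling is 60 implanted patients. The primary analysis uses the As Treated (AT) set (Section 11.3). This can slightly exceed 60, because only patients who leave the procedure room with the valve in place count toward the 60 (Section 6.3.2).

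On censoring, Section 11.3 says "AT patients that did not receive the SAPIEN XT valve will be censored at 30 days or at resolution of any AE". Section 6.3.3.6 says that patients who do not receive and retain the valve "will be followed up until the 30-day assessment or resolution of any AE for safety purposes".

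**The concern.** Greenwood's variance is built only from the times at which deaths occur. With no deaths it is zero, so the prescribed interval either shrinks to a point at 0% or cannot be calculated. This is a property of the stated method, and choosing a transformation in the SAP would not remove it. Only a zero-event rule or a different interval would.

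The interval carries weight because the study is single-arm with no hypothesis test, and its data are to be submitted for Chinese regulatory approval (Section 2.1). The mortality estimate and its precision are therefore the primary result. A 0%-0% interval would claim certainty that 50-60 patients cannot give. A replacement chosen after seeing zero deaths would be post hoc.

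**Working it through.** **Inputs.** n = 50 and 60 (Sections 5 and 11.1). The protocol sets no expected mortality, so two background rates from Section 2.2.2 serve as assumptions. The first is 3.4% at 30 days, from the TAVI arm of the high-risk randomized cohort with the earlier SAPIEN valve. The second is 2.1%, for a later device, of which the text says "its TF delivery has demonstrated the lowest rates of death, stroke, and major vascular complications (2.1, 1.0 and 4.2%, respectively) for any SAPIEN THV"; no time point is given there, so reading it as a 30-day rate is a further assumption. A two-sided 95% level is also assumed. There is no stated figure to reproduce, since the sample size has no statistical inputs.

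**Step 1: Greenwood with no deaths.** Var(S) = S² × Σ d/[r(r − d)], summed over death times, with d deaths among r at risk. With no deaths the sum is empty, S = 1 and SE = 0.
- Plain: 0 ± 1.96 × 0 gives 0%-0%.
- Log: 1 − 1 × exp(±1.96 × 0) gives 0%-0%.
- Log-log needs log(−log 1) and logit needs log(1/0); neither exists.

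Censoring does not change this, because the sum stays empty whatever the number at risk. As a check on the formula, 2 deaths in 60 without censoring gives SE = √[(2/60)(58/60)/60] = 0.0232, the ordinary binomial value.

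**Step 2: chance of no deaths, (1 − p)ⁿ.**

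| Assumed rate | n = 50 | n = 60 |
|---|---|---|
| 2.1% | 0.979⁵⁰ = 34.6% | 0.979⁶⁰ = 28.0% |
| 3.0% | 21.8% | 16.1% |
| 3.4% | 0.966⁵⁰ = 17.7% | 0.966⁶⁰ = 12.5% |
| 4.0% | 13.0% | 8.6% |
| 5.0% | 7.7% | 4.6% |

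**Step 3: what zero deaths is compatible with.** The exact upper limit is 1 − 0.025^(1/n): 7.1% for 0/50 and 6.0% for 0/60. If one patient is censored before day 30 and nobody dies, the limit based on the 49 or 59 still at risk is 7.3% or 6.1%. Greenwood still gives 0%-0%.

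**Step 4: one to three deaths, 95% upper limits (no censoring).**

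| Deaths | n = 50 plain | n = 50 exact | n = 60 plain | n = 60 exact |
|---|---|---|---|---|
| 1 | 5.9% | 10.6% | 4.9% | 8.9% |
| 2 | 9.4% | 13.7% | 7.9% | 11.5% |
| 3 | 12.6% | 16.5% | 10.5% | 13.9% |

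The plain lower limit is negative in all six cases. Log-log errs the other way: for 1 death its upper limit is 13.4% (n = 50) or 11.2% (n = 60).

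**Step 5: coverage of the plain nominal 95% interval, by binomial enumeration.**
- At 3.4%: 82.1% (n = 50) and 87.0% (n = 60). Zero deaths accounts for 17.7 of the 17.9 points of non-coverage and 12.5 of the 13.0. Given at least one death, coverage is 99.8% and 99.5%.
- At 2.1%: 65.3% and 71.8%.
- At 5%: 92.0% (n = 50) and 80.6% (n = 60). For n = 60 the shortfall comes mainly from the single-death result, whose upper limit of 4.9% just misses 5%.

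**The case against.** The arithmetic is not in dispute. The case against rests on five points.

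- **The SAP may already have a zero-event rule.** It may, and its absence cannot be shown from the available text. But Section 11.5 already fixes the method, so a SAP with another interval would depart from the protocol unless the two are aligned.
- **At least one death is the more likely result.** This stands: at 3.4%, the only background rate tied to 30 days, it happens 82-87% of the time. The 35% end of the range depends on the 2.1% figure for a later device. At an illustrative AT size of 66, the chance of no deaths at 3.4% falls to 10.2%.
- **Nothing is decided on this interval.** This also stands. The listings would show 0 deaths and the denominator, from which an informed reader could work out the exact limit. The harm is limited to misstated precision.
- **A one-line zero-event rule would be enough.** At 3.4% that is nearly true, since low counts add almost nothing to the shortfall. At 5% with n = 60 it is not: a single death, with probability 14.6%, is the main source of non-coverage. Replacing the interval outright covers both situations at about the same cost.
- **The censoring wording is a separate matter.** It does not cause the collapse. It matters here only because it decides which replacement interval applies.

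**Conclusion.** The concern holds and should be fixed. The interval prescribed for the primary endpoint is 0%-0% or undefined if nobody dies, and no transformation repairs it. At assumed rates of 2.1% to 3.4% this has a probability of about 13% to 35% with 60 to 50 patients, and less than 8% if the true rate is 5% or more. In that event the correct statement is an upper limit of about 6% to 7%, above both background rates. The size depends on those assumed rates, which come from other valve generations, on the assumed 95% level, and on no zero-event rule existing in the SAP that was not available. The problem affects how the main safety result is reported; it does not affect a success criterion, the point estimate or the conduct of the study.

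**What to change.** In Section 11.5, and in the same terms in the SAP, replace the Greenwood limits for 30-day mortality as follows:

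- If every AT patient has known vital status at day 30, report deaths over patients with a two-sided 95% Clopper-Pearson interval.
- If any patient is censored before day 30, keep the Kaplan-Meier estimate and use the beta product confidence procedure, which remains valid with zero events.

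State the confidence level. Reconcile Sections 11.3 and 6.3.3.6 on whether AT patients without the valve can be censored before day 30, since Section 6.3.3.6 can be read as requiring follow-up to at least that day. If the SAP already contains a zero-event rule, bring Section 11.5 into line with it.

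The cost is one or two sentences, with no change to conduct, data collection or sample size. The price is a wider, somewhat conservative interval: Clopper-Pearson coverage is 99.3% (n = 50) and 98.4% (n = 60) at 3.4%, and 97.9% and 99.1% at 2.1%.

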5.2 Exclusion Criteria

Patients must not meet any of the Exclusion Criteria in order participate in the study

- Evidence of an acute myocardial infarction ≤ 1 month (30 days) before the intended treatment [(defined as: Q wave MI, or non-Q wave MI with total CK elevation of CK-MB ≥ twice normal in the presence of MB elevation and/or troponin level elevation (WHO definition)].
- 2. Aortic valve is a congenital unicuspid or is non-calcified.
- 3. Aortic valve is bicuspid and the patient is less than 60 years old, or the aortic valve is bicuspid with no raphe (Sievers classification type 0) [42]
- 4. Anomalous coronary artery that would interfere with proper placement of the valve.
- 5. Mixed aortic valve disease (aortic stenosis and aortic regurgitation with predominant aortic regurgitation >3+).

- 6. Pre-existing mechanical or bioprosthetic valve in any position.
- 7. Any therapeutic invasive cardiac procedure resulting in a permanent implant that is performed within 30 days of the index procedure. Implantation of a permanent pacemaker or ICD is not considered exclusion criteria.
- 8. Any patient with a balloon valvuloplasty (BAV) within 30 days of the procedure (unless BAV is a bridge to procedure after a qualifying echocardiogram).
- Leukopenia (WBC < 3000 cell/mL), acute anemia (Hgb < 9 g/dL), Thrombocytopenia (Plt < 50,000 cell/mL).
- 10. Renal insufficiency (creatinine > 3.0 mg/dL) and/or renal replacement therapy at the time of screening.
- 11. Untreated clinically significant coronary artery disease requiring revascularization.
- 12. Emergency interventional/surgical procedures within one month (30 days) prior to the TAVI procedure.
- 13. Hypertrophic cardiomyopathy with or without obstruction (HOCM).
- 14. Severe ventricular dysfunction with LVEF < 20%.
- 15. Echocardiographic evidence of intracardiac mass, thrombus or vegetation.
- 16. Active upper GI bleeding within 3 months (90 days) prior to procedure.
- 17. A known contraindication or hypersensitivity to all anticoagulation regimens, or inability to be anticoagulated for the study procedure.
- 18. Stroke or transient ischemic attack (TIA) within 3 months (90 days) of the procedure.
- 19. Estimated life expectancy < 12 months (365 days) due to carcinomas, chronic liver disease, chronic renal disease or chronic end stage pulmonary disease.

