6.3.3.5 Discharge Visit

The following data will be collected for all study patients before discharge from the index hospitalization. If patient is discharged over a weekend, the discharge tests may be completed on the last weekday prior to discharge. For patients that are discharged within the 48 hours of exiting the cath lab / operating room, it is not required to repeat tests collected during the Post Procedure period that are also required for the Discharge visit.

- Pertinent physical examination [include blood pressure, weight and all major systems findings]
- Current cardiac medications and all medications given for cardiovascular effect
- NYHA functional classification
- CSS Angina Classification
- Adverse events
- Neurological assessments
 - o NIHSS
 - o MRS
- Clinical Laboratory Test
 - o Blood count (hemoglobin, hematocrit, platelet count, white blood cells)
 - PTT or PT/INR
 - o Creatinine
- 12-Lead ECG
- Comprehensive TTE. If not adequate, a TEE will be performed

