 - o Blood count (hemoglobin, hematocrit, platelet count, white blood cells)
 - o Creatinine

- CK/CK-MB and/or troponins
- o Albumin
- 12-Lead ECG
- Comprehensive TTE. If not adequate, a TEE will be performed

For patients with abnormal findings related to valve integrity and position and patients with adverse events related to worsening valve function, fluoroscopic imaging of the implanted valve will be completed.

6.3.3.6.2 6 Month Visit

All patients will undergo the following assessments within the 6 Month follow-up period:

- Adverse events
- Current cardiac medications and all medications given for cardiovascular effect

The 6 month visit may be completed via a telephone conversation with a delegated study team member. The telephone call must be documented in the patient's study records.

6.3.3.6.3 1 Year Visit

All patients will undergo the following assessments within the 12 Month follow-up period:

- Pertinent physical examination [include blood pressure, weight and all major systems findings]
- Adverse events
- Current cardiac medications and all medications given for cardiovascular effect
- NYHA functional classification
- CSS Angina Classification
- 12-Lead ECG
- Comprehensive TTE. If not adequate, a TEE will be performed

For patients with abnormal findings related to valve integrity and position and patients with adverse events related to worsening valve function, fluoroscopic imaging of the implanted valve will be completed.

6.3.3.6.4 2-5 Year Annual Follow-up Visit

All patients will undergo the following assessments within the 2-5 Year annual follow-up period:

- Pertinent physical examination [include blood pressure, weight and all major systems findings]
- Adverse events
- Current cardiac medications and all medications given for cardiovascular effect

- NYHA functional classification
- CSS Angina Classification
- Comprehensive TTE. If not adequate, a TEE will be performed

For patients with abnormal findings related to valve integrity and position and patients with adverse events related to worsening valve function, fluoroscopic imaging of the implanted valve will be completed.

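### Section 11.5 plans paravalvular regurgitation as a shift from baseline, but no patient has a prosthesis at baseline; the shift should start from the discharge echo

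*Combined protocol and SAP*

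**What the plan says.** Section 11.5 (Endpoint Analysis) has the core laboratory analyse the echocardiograms for the "degree of total aortic valve regurgitation (TVR) and paravalvular aortic valve regurgitation (PAR) according to the VARC-2 definitions". The next sentence opens by pointing back to those data, adds other categorical variables such as NYHA class, and says that they "will also be presented as shift from baseline for each of the pre-specified follow-up periods". Its opening words can only refer to the two regurgitation grades just named, so both total and paravalvular regurgitation are to be shown as change from baseline. No section names another reference visit for either.

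Section 5.2, criterion 6, excludes patients with this condition: "Pre-existing mechanical or bioprosthetic valve in any position". Section 6.3.3.1 (Screening) schedules a TTE within 60 days before the procedure, with TEE as the alternative. The Baseline visit list in Section 6.3.3.2 contains no echocardiogram.

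After implant, Section 6.3.3.5 (Discharge Visit) requires: "Comprehensive TTE. If not adequate, a TEE will be performed". Section 6.3.3.6 repeats that requirement at 30 days, 1 year and each annual visit to 5 years. Section 11.5 also promises frequency tables or proportions for discrete variables, tabulation of clinically relevant baseline and follow-up variables, and patient listings. It leaves further detail to a Statistical Analysis Plan.

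**The concern.** A paravalvular leak runs around an implanted prosthesis. A patient who has no prosthesis cannot have one, so the quantity whose change is to be tabulated does not exist at the visit chosen as its reference.

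What is lost is the course of the leak after implant. Echo valve performance, with paravalvular and central regurgitation named, is one of the two efficacy endpoints in Section 4.2, and echo follow-up runs to 5 years. Section 2.2.2 gives a reason to care about that course, noting that "a late association between residual PAR and mortality has been subsequently revealed". The useful question is whether a leak seen soon after implant stays, shrinks or grows in the same patient. The planned shift table cannot answer it, and Section 11.5 plans no other within-patient table.

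**Working it through.** The plan gives no figure to reproduce, so the check is one of structure.

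**Inputs.** Variables and reference visit: Section 11.5. State before implant: Section 5.2 criterion 6 and the screening TTE in Section 6.3.3.1. Echoes after implant: Sections 6.3.3.5 and 6.3.3.6. Imaging at the procedure itself is a supra-aortic angiogram or a TEE (Section 6.3.3.3.3), so it is not one common echo reference. The first TTE scheduled for every patient with the valve in place is the one at discharge. The number of grades is my assumption: four (none/trace, mild, moderate, severe). The argument does not depend on it.

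**Step 1: paravalvular shift from baseline.** Let n(b, f) be the number of patients with baseline grade b and follow-up grade f among N patients read at a visit.

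- If baseline is recorded as not applicable, no n(b, f) exists and there is no table.
- If baseline is set to none for everyone, n(none, f) = n(f) and every other row is zero. Of 4 × 4 = 16 cells, 4 can be filled and 16 − 4 = 12 must be empty. The row percentages n(none, f)/N are the follow-up frequencies. The number of patients with a lower grade than at baseline is 0 whatever the data.

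**Step 2: paravalvular shift from the discharge TTE.** All 16 cells can be filled: 6 with a lower grade than at discharge, 4 unchanged and 6 higher. That table can show regression, stability or progression.

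**Step 3: do the planned frequencies already show this?** They show the group at each visit, but deaths change who is in the group. Take an illustration with assumed numbers:

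- 10 of 60 patients have a moderate paravalvular leak at discharge: 10/60 = 16.7%.
- 6 of those 10 and 20 of the other 50 die before a later visit: 6 + 20 = 26 deaths, so 60 − 26 = 34 survivors. (26/60 = 43.3%, close to the 44.2% three-year mortality that Section 2.2.2 cites for the TAVI arm of the randomised trial in high-risk patients.)
- No survivor's grade changes. Moderate leak among survivors: (10 − 6)/34 = 4/34 = 11.8%.

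The frequency falls from 16.7% to 11.8% although no valve changed. The shift from a baseline of none gives the same 4/34. The shift from discharge puts all 34 survivors on the diagonal, which is the true picture.

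**Step 4: total regurgitation.** Here both grades exist: native regurgitation at screening and prosthetic regurgitation afterwards. The shift can be computed and shows the net change in regurgitation that the patient carries. It compares two different valves, so it does not measure how the prosthesis performs over time.

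**The case against.** The strongest reply is that the shift is an extra. Section 11.5 says *also*, and absolute grades, frequencies and listings are planned anyway. With a constant baseline the paravalvular table is redundant rather than misleading, and it cannot flatter the device. Neither efficacy echo results at 30 days nor device success refers to baseline. A reader could follow single patients through the listings, and the reference visit might be set in the Statistical Analysis Plan, whose further detail is not in the document available. All of this limits the consequence. It does not supply a baseline for paravalvular regurgitation, and listings do not replace a planned table. As written, Section 11.5 would carry its reference visit into the later plan.

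Two stronger readings are tempting, and the documents do not support them.

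A reader might infer that the total-regurgitation shift would credit a leaking prosthesis with improvement. Criterion 5 removes only mixed disease described as "aortic regurgitation with predominant aortic regurgitation >3"+, so native regurgitation up to 3+ may enter, and such a patient might end with a moderate prosthetic leak. But Section 11.5 scores no one as improved. A shift table would still show that patient in the moderate column, and the documents never map the plus scale to mild, moderate and severe. On the assumed four grades, 8 cells end in moderate or severe and so fail device success. Of these, 1 is a lower grade than baseline, 2 are unchanged and 5 are higher. No baseline prevalence of native regurgitation is given, so the number of patients in any such cell cannot be stated.

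A reader might also infer that a shift is promised at 6 months, where none is possible: "The 6 month visit may be completed via a telephone conversation", and only adverse events and medications are collected. That reads the follow-up wording too literally. NYHA class is not collected at that visit either, and the natural meaning is the visits at which each variable is measured.

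**Conclusion.** The point holds for paravalvular regurgitation. Its planned shift from baseline is undefined, or is a single row that copies the follow-up frequencies, for every implanted patient. That follows from criterion 6 and the visit schedule and needs no assumption about grades or prevalence; the four-grade scale and the survival illustration serve only to show the effect.

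The size is modest. The defect lies in a descriptive, additional display of secondary data. All-cause mortality at 30 days, device success and the absolute regurgitation grades at 30 days are unaffected. The loss is the within-patient course of the leak over 5 years, which visit-by-visit frequencies cannot show once patients die or miss echoes. The total-regurgitation shift is a legitimate display of net burden and needs only a clear label. The correction is worth making because the better table uses echoes that are already scheduled.

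**What to change.** In Section 11.5, and in the table shells of the Statistical Analysis Plan:

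- Replace the paravalvular shift from baseline with a shift from the discharge TTE to 30 days, 1 year and each annual visit to 5 years. Count patients with a readable study at both visits, and state how many lack one. Keep the absolute grade at every echo visit beside it.
- Keep the total-regurgitation shift from screening if wanted, with its baseline labelled as native valve and a note that it shows net regurgitant burden and is not a measure of prosthesis performance.
- Leave the NYHA shift from baseline as it is.

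The cost is wording; no visit or echo is added. The sponsor should confirm that the discharge TTE is read by the core laboratory, so that both ends of the shift come from the same reader. The one drawback is that a patient without a discharge echo has no shift value, though the absolute grades at later visits are still reported.
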